2.8. Analysis Sets

2.8.1. Efficacy Analysis Set(s)

The all treated analysis set will consist of all subjects who receive at least 1 dose of daratumumab. This analysis set will be used for efficacy analysis unless otherwise stated.

The response evaluable analysis set will consist of all subjects who satisfy all of the following:

- Received at least 1 dose of study drug;
- Had a baseline and at least 1 post-treatment disease evaluation.

Response evaluable analysis set will be used for the efficacy analyses at interim analysis.

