3. STUDY DESIGN AND RATIONALE

3.1. Overview of Study Design

This is an open label, single arm, multicenter, Phase 2 study to evaluate the efficacy and safety of daratumumab monotherapy in subjects with relapsed and refractory extranodal NKTCL, nasal type. The study is a Simon's 2-stage design with up to 32 subjects to be enrolled. Following that, additional patients (ie, approximately 35 patients) may be enrolled in an expansion phase.

Subject participation will include a Screening Phase, a Treatment Phase, and a Follow-up Phase. The Screening Phase will be up to 21 days prior to Cycle 1, Day 1. Prior to enrollment, diagnosis of NKTCL must be verified by the sponsor from the local pathology report. Before enrollment to the study, sites will be required to provide archival or fresh tumor samples for assessment of CD38 expression. Fresh biopsy samples are preferred if available. Otherwise, archived formalin-fixed, paraffin-embedded (FFPE) blocks/slides are also acceptable.

The Treatment Phase will extend from Cycle 1, Day 1 until study drug discontinuation. After the first dose, disease evaluations will occur every 8 weeks for the first 6 months and thereafter, every 16 weeks. Subjects will be monitored for safety and assessed for PK and immunogenicity according to the scheduled assessments in the Time and Events (T&E) schedules ([T&E Schedule](#) and [T&E Schedule: PK and Immunogenicity](#)). Subjects will be treated until PD, unacceptable toxicity, or other reasons as listed in the protocol. End-of-Treatment (EoT) Visit is to occur within 30 days (+7-day window) after the last dose of all study treatments.

The Follow-up Phase will begin once a subject discontinues study treatment, and will continue until death, lost to follow up, consent withdrawal for study participation, or end of study, whichever occurs first. The follow-up schedule is presented in the [T&E Schedule](#).

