4.1. Inclusion Criteria

Each potential subject must satisfy all of the following criteria to be enrolled in the study:

1. At least 18 years of age
2. Documented as histologically confirmed extranodal NK/T-cell lymphoma, nasal type according to the World Health Organization (WHO) classification,^{10,13,20} and the pathology report will be verified by the Sponsor.
3. Criterion modified per Amendment 1:
 - 3.1 Failed (relapsed or refractory after achieving complete or partial remission) at least 1 line of chemotherapy, and who, according to treating physician or investigator, is not candidate to receive other treatment modalities.
4. Criterion modified per Amendment 1:
 - 4.1 At least 1 measurable site of disease (see Section 8.2.1), which should be positive ¹⁸F-fluorodeoxyglucose (FDG) uptake in nodal or extranodal sites on positron emission tomography (PET) scan.
5. ECOG performance status score of 0, 1 or 2. (refer Attachment 1) and life expectancy ≥ 3 months.
6. Subject must have pretreatment clinical laboratory values meeting the following criteria during the Screening Phase:
 - a. hemoglobin ≥ 7.5 g/dL (≥ 4.65 mmol/L) without transfusion support within 7 days;
 - b. absolute neutrophil count (ANC) $\geq 0.75 \times 10^9/L$ (ie, $\geq 750/\mu L$) without growth factor support within 7 days;
 - c. platelet count $\geq 50 \times 10^9/L$ without transfusion support within 7 days;
 - d. aspartate aminotransferase (AST) ≤ 2.5 x upper limit of normal (ULN);
 - e. alanine aminotransferase (ALT) ≤ 2.5 x ULN;
 - f. total bilirubin ≤ 1.5 x ULN, except in subjects with congenital bilirubinemia, such as Gilbert syndrome (in which case direct bilirubin ≤ 1.5 x ULN required);
 - g. calculated creatinine clearance of ≥ 30 mL/min (refer Attachment 5: Calculation of Creatinine Clearance using Cockcroft-Gault formula);
7. Criterion modified per Amendment 1:
 - 7.1 Women of childbearing potential must commit to either abstain continuously from heterosexual sexual intercourse or to use 2 methods of reliable birth control simultaneously. This includes one highly effective form of contraception (tubal

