10.1. Subject Information

The primary analysis population is the safety population, which will include all treated subjects. The pharmacokinetic analyses will be performed on the pharmacokinetic evaluable population. Continuous variables will be summarized using descriptive statistics such as mean, SD, and range. Categorical variables will be summarized using frequency tables. For time-to-event variables, the Kaplan-Meier method will be used for descriptive summaries.

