1.4. Sample Size Justification

The study is designed to evaluate the effect of daratumumab on ORR utilizing Simon's 2-stage design. The null hypothesis is that ORR is at most 15%, and the alternative hypothesis is that ORR is at least 30%. With a 1-sided alpha of 10%, and a power of 78%, a total of 32 subjects are to be enrolled into the study. The stage 1 analysis is to be performed when approximately 15 subjects are enrolled in the study and have sufficient data for response evaluation. The futility criterion of ORR is defined as when at most 1 out of 15 subjects have achieved CR/ PR after stage 1 according to Simon's 2-stage design. Future enrollment into stage 2 may be terminated if it is determined during the first stage that the treatment group is considered as ineffective or not well tolerated. If study proceeds to second stage with a total of 32 subjects with 2 stages combined, the null hypothesis is to be rejected if 8 or more responders are observed.

To achieve 1-sided alpha of 2.5% and a power of 80%, additional patients (ie, up to 35 patients) may be enrolled in an expansion phase to confirm the clinical response rate of daratumumab if supported by emerging data.

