5. EFFICACY

5.1. Analysis Specifications

The analysis of efficacy will be based on BICR for all treated population. Sensitivity analysis will be performed based on investigators' assessment.

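### Does counting the interim futility rule on response-evaluable subjects, and the final rule on all treated subjects, upset the two-stage design?

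*SAP*

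**What the plan says.** SAP 2.8.1 defines two efficacy sets. All treated is the default. The response-evaluable set adds a condition: "Had a baseline and at least 1 post-treatment disease evaluation". The same section states that the "Response evaluable analysis set will be used for the efficacy analyses at interim analysis".

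The sample-size text (SAP 1.4, mirrored in Protocol 10.2) times stage 1 by a looser phrase: "The stage 1 analysis is to be performed when approximately 15 subjects are enrolled in the study and have sufficient data for response evaluation". For the end of stage 2 it says that "the null hypothesis is to be rejected if 8 or more responders are observed" among 32 subjects, without naming an analysis set in that sentence. SAP 5.1 supplies the set: "The analysis of efficacy will be based on BICR for all treated population". Protocol 10.1 agrees: "The primary analysis population is the safety population, which will include all treated subjects".

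SAP 3 and Protocol 10.9 set the interim at about 15 subjects with at least one dose and at least one post-baseline evaluation, and call the futility boundary non-binding. Protocol 3.1 fixes the scan schedule: "After the first dose, disease evaluations will occur every 8 weeks for the first 6 months and thereafter, every 16 weeks". The sentence on terminating the study joins its two conditions with *and* in Protocol 3.1 and SAP 1.2, but with *or* in Protocol 10.9 and SAP 3.

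**The concern.** A Simon design is normally computed as if the first 15 subjects are part of the final 32 and each has a known response. Here a subject who dies or withdraws before the week-8 scan drops out of the first denominator and stays in the second. That makes the interim count look better than the all-treated count and makes stopping for futility less likely.

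There is also a pull the other way. One evaluation is enough to enter the set, so some responses that would appear later are not yet visible, and this makes stopping more likely. The phrase about sufficient data is not defined where it stands, and no planned interim output shows how many treated subjects were left out. If the effects were large, the 78% power would not describe the trial being run, and the futility look would protect subjects less than it appears to.

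**Working it through.** **Inputs.** From SAP 1.4 and Protocol 10.2: p0 = 0.15, p1 = 0.30, n1 = 15, N = 32; futility at ≤1 response, rejection at ≥8. The documents give no share *d* of treated subjects without a later evaluation and no share *f* of responses visible at a first read. Both are assumed: *d* = 5%, 10%, 20%; *f* = 80%, 70%.

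**1. The plan's own figures.** With b(x; n, p) the binomial probability,

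P(reject) = Σ over x = 2..15 of b(x; 15, p) × P(Bin(17, p) ≥ 8 − x).

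This gives 9.38% at p = 0.15 and 78.09% at p = 0.30, so the stated 10% limit and 78% power reproduce.

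**2. Ceiling on type I error.** If the futility rule is ignored, P(Bin(32, p) ≥ 8) = 9.58% at 0.15 and 78.82% at 0.30. A futility stop can only remove rejections, so 9.58% bounds the type I error for any choice of interim set.

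**3. Chance of meeting the futility rule, as designed.** (1 − p)^15 + 15p(1 − p)^14:
- p = 0.15: 0.0874 + 0.2312 = 31.9%
- p = 0.30: 0.0047 + 0.0305 = 3.5%

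**4. Loss only, with 15% and 30% read as all-treated rates.** The rate among evaluable subjects is q = p/(1 − d), and the futility chance is P(Bin(15, q) ≤ 1). For power, K subjects without evaluation accrue while 15 evaluable ones are found (K negative binomial), which leaves 17 − K subjects responding at rate p.

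| d | q (15% / 30%) | Futility met (15% / 30%) | Type I error | Power |
|---|---|---|---|---|
| 0 | 0.150 / 0.300 | 31.9% / 3.5% | 9.38% | 78.1% |
| 5% | 0.158 / 0.316 | 29.0% / 2.7% | 9.44% | 78.4% |
| 10% | 0.167 / 0.333 | 26.0% / 1.9% | 9.49% | 78.6% |
| 20% | 0.188 / 0.375 | 19.8% / 0.9% | 9.55% | 78.8% |

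The first 15 treated cannot contain more responders than the first 15 evaluable. The two counts therefore disagree in one direction only, and the frequency is the difference between columns. At a 15% rate and 20% loss it is 31.86 − 19.81 = 12.05%; at 10% loss, 31.86 − 25.96 = 5.90%; at 5% loss, 2.9%. At a 30% rate the figures are 2.7%, 1.6% and 0.9%.

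**5. Loss only, with 15% and 30% read as evaluable-subject rates.** The interim chances stay at 31.9% and 3.5% whatever *d* is. Power falls, because the final count is on all treated at rate p(1 − d). It is 66.3% at 10% loss and 51.4% at 20%. Counting all treated at both looks gives 65.8% and 50.8%, so changing the interim set would recover nothing.

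**6. Loss plus an early read (reading of step 4).** Results are futility chance at 15% / at 30% / power.

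| d, f | 8 of 15 already mature | All 15 with one read only |
|---|---|---|
| 10%, 80% | 31.4% / 3.4% / 78.0% | 38.7% / 6.2% / 76.7% |
| 10%, 70% | 34.4% / 4.3% / 77.6% | 46.4% / 10.3% / 74.2% |
| 20%, 80% | 24.9% / 1.7% / 78.5% | 31.9% / 3.5% / 77.8% |
| 20%, 70% | 27.7% / 2.3% / 78.3% | 39.6% / 6.6% / 76.2% |

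In the middle column power stays within about half a point of the design value. The last column needs near-simultaneous accrual of all 15.

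**The case for a change.** The best case for a change is that Protocol 15.1 presents the futility look as a way to limit exposure, and that a non-binding rule depends on judgement. At 20% loss about 15/0.8 = 18.8 subjects are treated to find 15 evaluable, so a count of 2 in 15 could hide nearly four unscanned subjects.

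Such loss is not absurd. Protocol 1 cites a median survival of about 8 months for all patients with this disease. Under exponential survival, 8 weeks (1.84 months) gives 1 − 0.5^(1.84/8), about 15% dead before the first scan. Relapsed disease would raise this, and the entry requirement of at least 3 months' life expectancy would lower it. One descriptive table would show the excluded subjects at almost no cost.

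Part of this stands: the denominators do differ, and such a table would be useful to read. It does not amount to a fault in the plan. SAP 3 already has the interim weigh efficacy together with safety and biomarker data, and SAP 2.8.2 puts safety on all treated subjects, so early deaths are within what is reviewed. Protocol 8.2.6 sends unscheduled scans to central review, so a subject who progresses on imaging before week 8 normally has an evaluation and stays in the set. The interim tables need not all be listed for an analyst to report how many treated subjects were not evaluable.

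The differing *and*/*or* wording is a genuine inconsistency and the four sections should be reconciled. The allowance in SAP 1.4 and Protocol 10.2 for ending enrollment over tolerability does not settle which form was meant, since a separate tolerability stop is compatible with either. Both forms only say that the study may be terminated, and no operating characteristic depends on the choice.

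**Conclusion.** No change to the plan follows. The interim set is a declared choice that agrees with the interim trigger, and requiring an evaluation before counting a subject in an early look is a fair trade-off. The final set is stated in SAP 5.1 and Protocol 10.1; only the sentence with the 8-responder cut-off omits it. The undefined phrase about sufficient data is made operational by SAP 3, Protocol 10.9 and SAP 2.8.1, so a cross-reference is all that is missing.

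The final analysis is unaffected and type I error is at most 9.58% regardless of assumptions. The noticeable effect is on the chance of meeting a non-binding rule: at a 15% response rate, 31.9% by design and 29.0% to 19.8% under 5% to 20% loss, partly or fully offset by early reading. Power stays between 77.6% and 78.8% except where all 15 subjects have had a single read, when it could fall to 74.2%. These figures rest on assumed loss and visibility shares and on reading 15% and 30% as all-treated rates. On the other reading, loss alone leaves the interim chances unchanged, and the fall in power comes almost entirely from the all-treated final count.

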2.8.2. Safety Analysis Set

The all treated population will be used for safety analysis unless otherwise stated.

2.8.3. Pharmacokinetics Analysis Set

The PK analysis population will consist of all subjects who received at least 1 dose of daratumumab and have at least 1 sample collected during treatment to determine the concentration. This analysis set will be used for PK analysis.

2.8.4. Pharmacodynamics Analysis Set

The PD analysis population will consist of all subjects who received at least 1 dose of daratumumab and have at least 1 sample collected to determine PD biomarker response. This analysis set will be used for PD analysis.

2.9. Definition of Subgroups

No specific subgroup analysis will be performed.

3. INTERIM ANALYSIS AND DATA MONITORING COMMITTEE REVIEW

The study is designed with an interim analysis performed at the end of stage 1 when approximately 15 subjects have received at least one dose of study drug and had at least one post-baseline disease evaluation. Enrollment may be put on hold pending the decision of interim analysis unless the decision is clear based on available data before the interim analysis. The purpose of the interim analysis is to evaluate efficacy and safety data in stage 1 and facilitate the early preparation for the next step of development. The totality of efficacy (ORR), safety, and biomarker data will be analyzed at interim. The futility criterion of ORR is defined as at most 1 out of 15 subjects have achieved CR/PR after stage 1. This futility boundary is considered non-binding. Study may be terminated if the futility criteria are met or supported by the totality of data including biomarker and safety data.

In addition, at interim, the association between daratumumab activity and CD38 expression level will be explored. If a strong association between daratumumab activity and CD38 expression level is confirmed by emerging data or a low response rate is observed from stage 1 data due to low CD38 expression levels, then an enrichment strategy may be applied for stage 2 to mitigate the risk of low responses possibly attributed to low CD38 expression. The final analysis may be adjusted accordingly (e.g., primary analysis would be based on enriched population) if an enrichment strategy is applied in stage 2.

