8.2. Efficacy Evaluations

Disease evaluations will be performed at Screening, every 8 weeks (± 7 days) for the first 6 months and thereafter, every 16 weeks (± 7 days) until PD, withdrawal of consent from study participation, or the end of study.

Radiological and PET-CT scans should be performed and collected according to instructions from the independent imaging laboratory. A BICR will be performed to review all the imaging data and clinical information per pre-defined independent central review charter.

The central reviewers will assess disease status based on the Revised Criteria for Response Assessment: LUGANO classification, provided in [Attachment 6](#).¹² Similar methodology should be used for disease assessment at screening and throughout the course of the study. The treatment discontinuation due to PD should be based upon the real time reading results conducted by the central readers. On the basis of clinical information, if PD is confirmed, then for all such subjects, as soon as PD is confirmed by local assessment, the sponsor should be informed immediately.

In order to maximally reduce potential bias between different readers, rigorous methodology will be employed and thus, ensure robustness of the primary endpoint assessment of ORR which is based on BICR. All radiological scans and collected clinical information will be sent to a sponsor appointed Clinical Research Organization (CRO) for a real time BICR. All treatment decisions will be based on such timely central review result. Subjects who are determined to have progressed according to LUGANO classification by the investigator will have scans centrally reviewed for confirmation of objective disease progression. If PD is not confirmed after central review, daratumumab treatment should be continued until centrally documented PD. This procedure may not be followed if the clinical information of subject (eg, Pathologically demonstrated PD) is sufficient enough to demonstrate PD, for such cases, PD confirmation from sponsor study physician is also required.

Definition of Measurable Disease, Assessable Disease, Target Lesion, and Non-Target Lesion

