10.9. Interim Analysis

The study is designed with an interim analysis performed at the end of stage 1 when approximately 15 subjects have received at least one dose of study drug and had at least one post-baseline disease evaluation. Enrollment may be put on hold pending the decision of interim analysis unless the decision is clear based on available data before the interim analysis. The purpose of the interim analysis is to evaluate efficacy and safety data in stage 1 and facilitate the early preparation for the next step of development. The totality of efficacy (ORR), safety, and biomarker data will be analyzed at interim. The futility criterion of ORR is defined as at most 1 out of 15 subjects have achieved CR/PR after stage 1. This futility boundary is considered non-binding. Study may be terminated if the futility criteria are met or supported by the totality of data including biomarker and safety data.

In addition, at interim, the association between daratumumab activity and CD38 expression level will be explored. If a strong association between daratumumab activity and CD38 expression level is confirmed by emerging data or a low response rate is observed from stage 1 data due to low CD38 expression levels, then an enrichment strategy may be applied for stage 2 to mitigate the risk of low responses possibly attributed to low CD38 expression. The final analysis may be adjusted accordingly (eg, primary analysis would be based on enriched population) if an enrichment strategy is applied in stage 2.

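### The stage-1 futility count can be taken after a single scan, so the stated 78% power is not assured

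*SAP*

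**What the plan says.** **Interim trigger.** SAP section 3 sets the stage-1 analysis when "approximately 15 subjects have received at least one dose of study drug and had at least one post-baseline disease evaluation". Protocol sections 3.1 and 10.9 and SAP section 1.2 carry the same condition. The sample-size sections (protocol 10.2, SAP 1.4) put it differently: about 15 enrolled subjects with enough data to evaluate response. What counts as enough is not defined.

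**Futility rule.** Protocol section 10.9: "The futility criterion of ORR is defined as at most 1 out of 15 subjects have achieved CR/PR after stage 1". The boundary is declared non-binding. Protocol 10.9 and SAP 3 allow termination if the criterion is met *or* the totality of data supports it. Protocol 3.1 and SAP 1.2 say met *and* supported.

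**Final rule and power.** SAP section 1.4: "With a 1-sided alpha of 10%, and a power of 78%, a total of 32 subjects are to be enrolled into the study". At the end, "the null hypothesis is to be rejected if 8 or more responders are observed". The hypotheses are an ORR of at most 15% against at least 30%.

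**Response over time.** Protocol section 8.2 schedules evaluations every 8 weeks for 6 months and every 16 weeks after that. ORR (protocol 10.3.1, SAP 5.2.1) is the proportion achieving CR or PR by BICR, with no time limit. The primary analysis is about 6 months after the last first dose (protocol 3.1), so even the last subject can have scans at weeks 8, 16 and 24.

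**Analysis sets.** The interim uses the response evaluable set (SAP 2.8.1). The final analysis uses all treated subjects (SAP 5.1).

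**The concern.** The two-stage calculation treats response as one fixed outcome per subject, known at both looks. The trigger does not secure that. A first response at week 16 or 24 is missing from the stage-1 count but present in the final count. For a given set of 15 subjects, counting early can only lower the stage-1 number.

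At stake is a false futility signal for an active drug. The stage-1 boundary is low, so moving one or two responders to a later scan can decide whether it is met. The issue is how long each subject has been observed, which is separate from the choice of analysis set.

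**Working it through.** **Inputs.** From SAP 1.4 and section 3: n1 = 15, futility if the count is 1 or fewer, N = 32 (17 in stage 2), reject at 8 or more, p0 = 0.15, p1 = 0.30. Not in the documents, so assumed over a range: f, the share of eventual responders already CR or PR at the first scan; and m, the number of the 15 subjects who have only that scan when the count is taken. The other 15 − m are taken as fully ascertained.

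**Step 1: reproduce the stated power** (f = 1, boundary followed).

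Chance of a futility signal: P(X1 ≤ 1) = (1 − p)^15 + 15p(1 − p)^14. At p = 0.30 this is 0.00475 + 0.03052 = 0.0353.

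Power = Σ over x1 = 2 to 15 of P(X1 = x1 | 15, p) × P(X2 ≥ 8 − x1 | 17, p). At p = 0.30 this is 0.7809. At p = 0.15 the same sum gives a type I error of 0.0938. The stated 78% and the 10% ceiling are both met.

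**Step 2: late ascertainment, all 15 on one scan.** Each eventual stage-1 responder is visible with probability f, so the interim count is binomial with rate f × p.

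- f = 0.8, rate 0.24: 0.76^15 + 15 × 0.24 × 0.76^14 = 0.0163 + 0.0772 = 0.0935.
- f = 0.7, rate 0.21: 0.79^15 + 15 × 0.21 × 0.79^14 = 0.0291 + 0.1162 = 0.1453.

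For power, let x be the eventual stage-1 responders and y the visible ones, with y given x binomial(x, f). Sum P(x) × P(y | x) × P(X2 ≥ 8 − x | 17, p) over all x and all y ≥ 2. The final count uses x, not y.

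**Step 3: staggered entry.** Thin only the responders among the m one-scan subjects. Results at a true ORR of 30%, boundary followed:

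| One-scan subjects (m of 15) | f | Chance of count ≤ 1 | Power |
|---|---|---|---|
| any | 1.0 | 3.5% | 78.1% |
| 15 | 0.9 | 5.8% | 77.0% |
| 15 | 0.8 | 9.4% | 75.1% |
| 15 | 0.7 | 14.5% | 71.7% |
| 15 | 0.5 | 31.9% | 58.9% |
| 10 | 0.8 | 6.8% | 76.5% |
| 10 | 0.7 | 9.2% | 75.2% |
| 10 | 0.5 | 16.2% | 70.6% |
| 5 | 0.8 | 4.9% | 77.5% |
| 5 | 0.7 | 5.7% | 77.1% |
| 5 | 0.5 | 7.7% | 76.1% |

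With all 15 on one scan, power drops below 76% at f of about 0.84.

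**Step 4: boundary not enforced.** P(X ≥ 8 | 32, 0.30) = 0.7882, whatever f is. The matching type I error is P(X ≥ 8 | 32, 0.15) = 0.0958.

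**Step 5: type I error with the boundary followed.** With all 15 on one scan it falls from 9.4% to 8.7% (f = 0.8) and 8.1% (f = 0.7).

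**The case against.** A reader might infer that the trial does not deliver its 78% power. The documents do not support that, for four reasons.

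- **The boundary is non-binding and termination is discretionary.** If it is not enforced, power is 78.8%. A sponsor who sees one response with stable subjects still on treatment may already wait. This stands. However, the 78% matches the calculation with the boundary followed, and protocol 10.9 and SAP 3 let the count alone justify stopping.
- **The size rests on f, which the documents do not give.** At f = 0.9 the worst-case loss is about one point (78.1 − 77.0 = 1.1). The figures at f = 0.5 are arithmetic, not a prediction. This stands.
- **One evaluation is a minimum.** In a rare disease, accrual will probably be staggered and earlier subjects will have more scans. The table shows how far this shrinks the effect. It does not remove it.
- **The interim set drops treated subjects without a post-treatment evaluation, which tends to raise the interim rate.** As an illustration, suppose 15% of treated subjects are non-evaluable non-responders. The evaluable rate is then 0.30/0.85 = 0.353. At f = 0.8 the visible rate is 0.282, and the chance of 1 or fewer in 15 is 4.8% instead of 9.4%. That share is also an assumption, so this is a partial offset of unknown size.

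The sample-size sections' call for enough data to evaluate response could be read as a maturity condition. It is undefined, and the interim sections state one evaluation as the trigger, so it does not settle the matter.

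**Conclusion.** The point holds as a gap in the definition of the stage-1 count. The trigger permits counting after one scan of about 8 weeks, the final test counts later responses, and nothing says how subjects still pending are treated. The stated 78% is therefore not assured; it has not been shown to be missed.

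At a true ORR of 30% with the boundary followed, the loss from 78.1% is 3.0 points (f = 0.8) or 6.4 points (f = 0.7) if all 15 have one scan. It is 1.6 or 2.9 points if 10 do, and 0.6 or 1.0 points if 5 do. These figures rest on the assumed f and m and leave out the analysis-set offset. There is no inflation of type I error above the planned 10%. The remedy is a cheap improvement and should be made.

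**What to change.** In SAP section 3 and protocol section 10.9, define sufficient response data. Apply the 1-of-15 criterion only when each of the 15 subjects has one of the following:

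- a BICR response;
- BICR progression;
- death;
- an end of disease assessment (new anticancer therapy, withdrawal of consent or loss to follow-up);
- a second (week-16) evaluation that has been read.

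Stopping treatment should not by itself settle a subject's status, because protocol section 8.1.4 keeps subjects who discontinue before progression on scheduled scans. If the count is 1 or fewer with subjects pending, defer the decision until those scans are read.

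In SAP 1.4 and protocol 10.2, refer to this definition and state that the 78% assumes the boundary is followed and stage-1 responses are fully ascertained at the interim. Responses first seen at week 24 remain a small residual. Reconcile the *and*/*or* wording on termination at the same time.

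Cost: wording in both documents, with no added procedures. A futility decision may come up to about 8 weeks later, but only when the count is 1 or fewer with subjects pending. If enrolment is not held, more subjects may enter during that time.
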